12. Implementation factors of UTBC influencing medication continuity (Appendix K & L): These factors will be measured using the Adolescent and Parent Medication Barriers Scales (AMBS and PMBS) (Simons et al. 2007; Simons et al. 2010). Adolescents and parents respond using a 5-point Likert-like scale from “strongly disagree” to “strongly agree” to report perceived barriers to medication taking. Both the adolescent scale (17-items) and parent scale (16-items) have strong internal consistency for total score and the four factor-analytically derived subscales: ‘Disease frustration/adolescent issues’, ‘Regimen adaptation/cognitive’, ‘Ingestion issues’, and ‘Parent reminder’. For criterion-related validity, adolescents classified as non-adherent had significantly higher barrier scores than those classified as adherent. In prospective validation studies, the adolescent-perceived barriers of ‘Disease frustration/adolescent issues’ and parent-perceived barriers of ‘Regimen adaptation/cognitive issues’ were associated with poorer adherence to medication taking (Simons et al. 2010).
13. Medication Continuity: We will calculate the percentage of days covered with medicine based pharmacy dispensing records and verified by parent report of ADHD service use using the reliable Services for Children & Adolescents – Parent Interview (Eaton Hoagwood et al. 2004). This measures ADHD service use, including office visits and medication use. We have successfully obtained pharmacy dispensing records via parental permission for 95% (155/164) of subjects across 2 studies (R01 MH074770, K23 MH083027) ([name] et al. 2013; [name] et al. 2016). Pharmacy dispensing records provide an objective, unobtrusive, reliable measure that is a well-accepted proxy for medication consumption (Steiner et al. 1997) that was significantly correlated with the more expensive and invasive Medication Event Monitoring System (MEMSCap™) which uses a microprocessor in the medication container cap to record the day and time of each vial opening (Farley et al. 2003).
14. Medication Diversion: Self-report of giving away, trading, or selling ADHD medicine to someone for whom it was not prescribed will be collected via a confidential web-based survey used in past population-based studies of middle/high school students. (Boyd et al. 2007; McCabe et al. 2011a).
15. Client Satisfaction Questionnaire (CSQ) (Attkisson et al. 1982) is an 8-item unidimensional measure of client satisfaction with services. Psychometric properties, operating characteristics, and coefficient alpha (.93) are very strong for this measure which we will collect from adolescents and parents.
16. Decision Making Involvement Scale (DMIS) (Miller et al., 2012): is a 30-item scale to measure adolescent involvement in a decision. The five subscales are: “Child Seek” (child asks for an opinion or information from parent), “Child Express” (child expresses an opinion or information to parent), “Parent Seek” (parent expresses advice or opinion to child), “Parent Express” (parent expresses advice or opinion to child), and

“Joint/Options” (negotiation or brainstorming between parent and child). We will collect this measure from adolescents and parents.

DATA ANALYSIS

Hypothesis testing:

Each hypothesis examines part of the mechanism underpinning intervention impact on medication continuity.

Hypothesis #1: *Adolescents will use greater than 80% of relevant intervention components.* For each subject in the intervention group, we will calculate the proportion of **recommended** intervention components that were utilized by the subject during the study. The mean and 95% confidence interval (CI) will be computed to give a range estimate of the fidelity measure. To evaluate our hypothesis, we will utilize the computed CI to determine if 80% or greater is a plausible value, such that if the CI includes a value of 80% or greater we will reject the null hypothesis. We will also examine the temporal distribution of use for each of the recommended components.

Hypothesis #2: *Use of the intervention components will be related to improvements in the targeted UTBC factors.* Using a generalized linear model, we will test whether the intervention addressed the UTBC factors (i.e., pre-intention factor scales and ABMS/PBMS total and subscale scores). Model predictors will include a fixed effect indicator of time point (baseline or end of study). A significant effect of time point in the expected direction would indicate UTBC factor improvement.

Hypothesis #3: *Medication continuity will be higher in the intervention group compared to the control group.* We will compare the percentage of days covered with medicine using a two-sample t-test.

Hypothesis #4: *Pre-post changes in UTBC factors will be related to increases in medication continuity.* We will calculate the change score for each relevant UTBC factor (end of study minus baseline) and the change score for medication continuity (percentage of days covered at end of study minus percentage of days covered in the 12 months prior to study). We will model the association between change in UTBC factor scores (independent variable) with change in medication continuity (dependent variable) using generalized linear mixed model. A significant effect of change in UTBC factor scores (beta coefficient) in the expected direction would indicate changes in UTBC factor scores were associated with medication continuity improvement.

Exploratory analyses:

We will conduct descriptive analyses to characterize rates of diversion at baseline and at the end of study using a McNemar's test to see if rates differ. We will summarize responses to the client satisfaction questionnaire descriptively as this may facilitate future dissemination.

Power and Sample Size:

The study would require a sample size of 18 for each group (i.e. a total sample size of 36), to achieve a power of 80% and a level of significance of .05 (two sided), to detect a difference in means between the intervention and the control groups of 15.7% (i.e. 66.2% vs. 50.5%) on the percentage of days covered with medicine assuming a pooled standard deviation of 16.5. Due to the low intra-class correlations observed in previous studies of ADHD medication continuity (ICC = 0; [name] et al. 2018), the analyses will not account for the nesting of patients within physicians. We will recruit 44 patients to ensure that 36 are retained at the end of the study. A retention rate of 80% (36/44) is conservative in light of the 12-month retention rate of 92% achieved by [name] in his current trial. We will use a stratified blocked randomization procedure to ensure baseline medication continuity is evenly distributed in both arms.

Scientific Rigor:

The RCT is a rigorous design to test efficacy of our intervention. We will explicitly address whether the intervention engages the mechanism underlying medication continuity and therefore warrants further testing in a future larger trial. Our preliminary data strongly supports the importance of the problem, intervention targets identified, and the feasibility of the approach in our hands.

Randomizing at the patient level, introduces a risk of contamination because it is possible that physicians will have encounters with patients assigned to both intervention and control arms. We are taking several steps to mitigate this risk. First, we have designed the software so that intervention components can be selectively “turned on” for patients allocated to the intervention group. Second, most intervention components will be used directly by patients and parents. For example, teens might choose to receive daily text message reminders to take their medicine. Parents might choose to receive text message reminders to obtain refills. Teens and/or parents might watch videos about ADHD, medication, stigma, etc. Again, these features won’t be “turned on” for patients in the control group. Some intervention components, like medication experiments promote interactions between patient, parent, and pediatrician. Pediatricians will have awareness of these features and receive training on how to interact with families to discuss what they learned from conducting an experiment. That said, it is unlikely that families allocated to the control group will conduct such experiments if they don’t have access to this intervention component in the mehealth for ADHD software.

FACILITIES

Cincinnati Children’s Hospital is the performance site for this study.

POTENTIAL BENEFITS

Although we cannot guarantee a benefit to any individual participating pediatrician, adolescent, or parent, the intervention components we propose to integrate into the ADHD web portal are theory- and evidence-based strategies with significant support from the research and clinical literature. Thus, families randomized to receive the intervention have the potential to benefit from state-of-the-art treatment. Benefits of the study outweigh any potential risks because our interventions are likely to improve care and outcomes for children who receive them.

POTENTIAL RISKS, DISCOMFORTS, INCONVENIENCES, AND PRECAUTIONS

There is minimal risk to the participants in this study other than a potential for invasion of privacy. Because confidential information about study participants will be available to study staff, procedures to safeguard the confidentiality of this information are required. As an NIH funded study, a Certificate of Confidentiality protects the privacy of research subjects by prohibiting disclosure of identifiable, sensitive research information to anyone not connected to the research except when the subject consents. Additionally, several safeguards will be put in place. All data collected on pediatricians, adolescents, and parents will be assigned a unique code that will be linked to identifying information. The master coding sheet that will link the information will be kept in the study coordinator’s office under lock and key. In addition to assuring confidentiality of the research data, it is also critical that the confidentiality of the patient’s clinical information is protected in mehealth for ADHD. The HIPAA regulations and their application to this product will be clearly defined to ensure compliance within their guidelines. Mehealth for ADHD was designed with a procedure for encrypting and storing the

data in such a manner to only allow pediatricians to view identifiable data. This design employs a key-based encryption structure. This method does require extra security information to be maintained by the parties who are encrypting the data. For example, parties needing access to the data are assigned a "key" that is used to encrypt and decrypt the data in addition to a user ID. Such a key will be maintained by the PI and kept under lock and key. Implementation of additional methodologies to keep the confidential information off the server will be implemented including such methodology as ensuring the CCHMC server is secure (i.e., firewalled).

Data from this study may be submitted to the National Institute of Mental Health (NIMH) that allows researchers studying mental health and substance use to collect and share deidentified information with each other. If participants consent to have their information shared in the data repository, all personal information about research participants such as name, address, and phone number will be removed and replaced with a code number. Participants may decide at any point that they do not want to share their information to the NIMH data repository. If a family consents to have their data shared, the information required to create their deidentified code number will be collected during the phone screen by a member of the research team.

PROTECTION OF VULNERABLE POPULATION

Because children are being invited to participate in the study, the following procedures will be followed to avoid issues related to coercion or undue influence. First, study staff will review the assent form with participating children, in language appropriate for their intellectual functioning and developmental levels, and ask whether or not the child agrees to participate. Similarly, they will be told that they can opt not to participate or answer any questions which they do not want to answer at any time. This will be re-iterated whenever necessary.

RISK/BENEFIT ANALYSIS

The risks to participants are minimal and unlikely, largely stemming from the possibility of loss of confidentiality. We have instituted provisions to minimize this risk and will assure participants of the voluntariness of their participation and their right to withdraw participation at any time. We will also take appropriate steps to safeguard confidentiality. We would suggest that this study falls under the "Minimal Risk" category.

ALTERNATIVES

Participation in the present study is completely voluntary. The alternative to participation in the study is to choose not to participate in the study.

DATA SAFETY & MONITORING

Physicians, adolescents, and parents who agree to participate and are randomized to the intervention group will receive access to a version of the mehealth for ADHD that has been enhanced with new intervention components. Given that the risks to participants are minimal, there does not appear to be the need for an external monitoring board. Rather, the Drs. [name] (PI) and [name] (co-I) will assume primary responsibility for the ongoing monitoring of the data and safety of the study, and will provide reports of this with annual renewal application to the IRB and annual progress report to the sponsor. Both are experts in ADHD management, ADHD research, and have experience conducting practice-based research such as that proposed in this application. [name] has medical expertise related to pharmacotherapy of

children with ADHD to address study-related medical issues. All research staff will complete education in the protection of human research subjects.

Drs. [name] and [name] will continuously evaluate the project's performance, safety, and need to stop. Performance will be monitored by examining subject recruitment, comparison with targeted recruitment retention, protocol adherence, and quality of data collection procedures. This will primarily be accomplished in weekly staff meetings attended by Drs. [name] and [name].

Drs. [name] and [name] will be available at all times to address any safety issues. Any serious adverse events will be determined by Drs. [name] and [name] and reported to the IRB within 24 hours, specifying the nature of the event and outcome, if related to the study and if anticipated or not. If a serious adverse event as a result of participation in the study occurs, recruitment will be immediately discontinued until the serious adverse event has been reported to the IRB and the IRB has deemed it appropriate for the study to continue.

COST OF PARTICIPATION

There will be no costs to the subject for participating in this study.

PAYMENT FOR PARTICIPATION

Each parent/adolescent dyad will be compensated \$200 for the visit at the beginning of the study, and \$100 for the visit and surveys at the end of the study for a total of \$300 throughout the intervention. All payments will be made at the end of each visit to the parent. ClinCards will be used for all payments.

REFERENCES

- Ajzen, I. (1991). "The theory of planned behavior." Organ. Behav. Hum. Decis. Process. **50**: 179-211.

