9. Fidelity to intended use of intervention components: For each adolescent and parent, we will calculate the proportion of intervention components completed relative to the components that were recommended by the portal based on adolescent/parent responses to the assessment battery. For intervention components that are used once (e.g. trial on/off medicine), we will identify a portal data element to characterize intervention component completion. For intervention components that are used more than once (e.g. refill reminders, pill taking reminders, etc.), we will define "intended use" of the feature as use for at least 2 months since research suggests that, on average, it takes 2 months to develop a new habit (Lally et al. 2010). Mehealth for ADHD will capture and report on these data elements to characterize fidelity to the intended use of intervention components for each adolescent and parent.
10. Pre-intention factors of UTBC influencing medication continuity (Appendix G & H): Our measurement strategy for the adolescent and parent pre-intention factors closely follow well-developed procedures (Ajzen et al. 1981). We will use standard scales that have been used in hundreds of previous studies using the UTBC and closely related basic science theories. For example, an item to assess social norms would be "Most of the

people who are important to me think I should take ADHD medicine regularly.” Responses are on a 7-point scale from strongly agree (+3) to strongly disagree (-3). The internal consistency of items within each construct is good ($0.7 \leq \alpha \leq 0.9$) (Steele et al. 2005; Bentley et al. 2009; Cornelio et al. 2009; Boyko et al. 2011). For this study, we will assess pre-intention factors (i.e. expectations, social norms, self-concept/image, affect and emotions, and self-efficacy) framed around the behavior of “taking ADHD medicine regularly” following published methods (Francis et al. 2004) and informed by our prior qualitative research ([name] et al. 2009, 2012).

11. Behavioral Intentions (Appendix I & J): Teen and parent intention for teen to take ADHD medicine regularly will be measured using the standard measure of intention from the UTBC (Ajzen and Fishbein, 1981).

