Official Title of the study: **Randomized Controlled Trial of Web Based Tools to Improve Medication Continuity in Adolescents With ADHD**

NCT number: **NCT04386096**

Document name: **Statistical Analysis Plan**

Date of the document: **12/15/2021**

The results of the Web Based Tools study will be assessed as described in this document. This statistical analysis plan begins with an overview of the key components of the study, including its design, objectives, and outcomes measures. This is followed by a detailed description of the statistical analyses that will be utilized to address study hypotheses.

**1. Overview of study:** This study used a parallel group randomized control trial to test whether an intervention engages the proposed mechanism underlying medication continuity and improves outcomes. Adolescents and their parents that agreed to participate in the study were randomized to receive either the intervention (MeHealth for ADHD software with medication continuity tools) or the control group (MeHealth for ADHD software with no medication continuity tools). We used a stratified randomization procedure to ensure that the intervention and control groups were balanced with respect to the number of days covered with ADHD stimulant medication in the past year based on dispensing data. We planned to enroll a total of 44 adolescents aged 11-15 with ADHD with poor medication continuity from Cincinnati Children's Pediatric Primary Care Clinic (PPCC) in order to retain  $\geq 36$  subjects needed based on our sample size calculation.

**1.1 Study Objective:** Test a multi-component intervention that systematically identifies and targets aspects of the Unified Theory of Behavior Change (UTBC) model most relevant for each adolescent with poor ADHD medication continuity.

Working hypothesis 1: compared to the control group, the intervention group will have greater medication continuity as measured by number of days covered with medicine at the end of the study.

Working hypothesis 2: compared to the control group, the intervention group will have improved outcomes as measured by change in the Unified Theory of Behavior Change factors.

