### **1.3 Intervention Fidelity measures**

#### *Intervention group only*

- Fidelity to intended use of intervention components during the 4-month trial.
  - Proportion of intervention components completed relative to the components that were recommended by the portal based on adolescent/parent responses to the assessment battery.

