#### 2.3.4 Intervention Fidelity measures

##### *Intervention group only*

The following will be summarized as mean and full range:

- Proportion of intervention components completed relative to the component that were recommended by the portal based on adolescent/parent responses to the assessment battery.

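### Protocol Hypothesis 1 accepts use above 80% whenever the 95% CI merely reaches 80%; the later SAP makes fidelity descriptive but does not withdraw the rule

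*Protocol*

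**What the plan says.** In the Protocol, Data Analysis, Hypothesis #1 is stated as "Adolescents will use greater than 80% of relevant intervention components". The analysis set is the intervention arm. The plan for estimation is "The mean and 95% confidence interval (CI) will be computed to give a range estimate of the fidelity measure". The plan for the decision is "we will utilize the computed CI to determine if 80% or greater is a plausible value", and then "if the CI includes a value of 80% or greater we will reject the null hypothesis". The null hypothesis is not written out.

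Protocol outcome measure 9 says how the data arise: "Mehealth for ADHD will capture and report on these data elements to characterize fidelity to the intended use of intervention components".

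The SAP is dated 12/15/2021, ten months after the protocol (2/12/2021). It opens with "The results of the Web Based Tools study will be assessed as described in this document". Its two working hypotheses (section 1.1) concern medication continuity and the UTBC factors. Section 1.3 lists "Fidelity to intended use of intervention components during the 4-month trial" as an intervention-group measure, with no hypothesis and no threshold. Section 2.3.4 gives the whole analysis: "The following will be summarized as mean and full range". The SAP does not mention Hypothesis 1, the 80% criterion or a confidence interval for fidelity.

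**The concern.** The claim to be supported is a mean above 80%, so the natural null is 80% or less. Rejecting that null requires the whole interval to lie above 80%. The protocol requires only that the upper limit reach 80%. Its own word for this, plausible, describes a value that has not been ruled out, which is weaker than a value shown to be exceeded. Two things follow: an observed mean well below 80% can count as success, and a wider interval makes success easier.

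This rule is the only success criterion for fidelity in either document. If a report applies it, an interval straddling 80% would be written up as use above 80%. The protocol presents each hypothesis as testing part of the mechanism, and it looks to the mechanism results to judge whether a larger trial is warranted, so overstated use could colour that judgement. Separately, the SAP's summary gives no measure of precision for a mean based on about 20 adolescents.

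**Working it through.** **Can any null rescue the rule?**
- Null of at most 80%: rejection needs the lower limit above 80%.
- Null of exactly 80%: an interval containing 80% means not rejecting.
- Null of at least 80%: an interval reaching 80% means not rejecting.

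The rule is wrong under all three.

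**Inputs.** The documents give no error rate, power or SD for fidelity. Their one computed figure is the sample size for medication continuity: difference 15.7 points, SD 16.5, two-sided 0.05, 80% power. Per group, n = 2 × (1.960 + 0.842)² × 16.5² / 15.7² = 2 × 7.85 × 272.25 / 246.49 = 17.3, rounded up to 18. This reproduces the protocol's figure.

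For fidelity I use n = 22 (half of the 44 recruited), because the portal captures fidelity and a missed end-of-study survey need not remove it. The low case is n = 18 (retained per group). The fidelity SD is assumed to be 10, 20 or 30 points.

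**Formulas.** Half-width = t(0.975, n−1) × SD / √n, with t = 2.0796 for n = 22 and 2.1098 for n = 18. Example, n = 22 and SD 20: 2.0796 × 20 / 4.690 = 8.87. The lowest observed mean that passes is 80 minus the half-width, here 71.1.

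The probability of success is P(upper limit ≥ 80) = P(T′ ≥ −t(0.975, n−1)), where T′ is noncentral t with noncentrality (μ − 80)/(SD/√n) and μ is the true mean. At μ = 80 the noncentrality is 0, so the probability is 0.975 for any n and SD.

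| | SD 10 | SD 20 | SD 30 |
|---|---|---|---|
| Half-width, n = 22 | 4.43 | 8.87 | 13.30 |
| Half-width, n = 18 | 4.97 | 9.95 | 14.92 |
| Lowest passing mean, n = 22 | 75.6% | 71.1% | 66.7% |
| Lowest passing mean, n = 18 | 75.0% | 70.1% | 65.1% |
| Success at true mean 75%, n = 22 | 39% | 80% | 89% |
| Success at true mean 75%, n = 18 | 48% | 83% | 90% |
| Success at true mean 70%, n = 22 | 0.6% | 39% | 68% |
| Success at true mean 70%, n = 18 | 2% | 48% | 73% |

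**Check on boundedness.** Fidelity lies between 0 and 100%, so the rule was also simulated with beta-distributed data (200,000 runs). At a true mean of 70%, success was 0.2%, 39% and 74% (n = 22) and 1%, 50% and 80% (n = 18) for SD 10, 20 and 30. At a true mean of 80% it was 98.5% to 99.3%.

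**The case against.** The strongest reply is that the SAP has already dealt with this. It is the later document, it says results will be assessed as it describes, and it leaves fidelity with no null, threshold or test. It also omits other protocol analyses without comment (the Hypothesis 2 time-point model, the Hypothesis 4 change-on-change model, the McNemar test), so replacement by omission is its general habit. Anyone misled would have to pass over the SAP and revive a protocol sentence, and the reported mean would expose the problem to most readers. This largely stands, and it is why the point is minor. It does not close the gap: omission is not withdrawal, and the rule remains in the current protocol under its hypothesis-testing heading.

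A second reply is that the size rests on assumption. That also stands. At a true mean of 70%, false success runs from about 1% to 73% by t theory, depending on an SD that the documents do not give. At SD 30 the beta model is U-shaped and gives rates 6 to 7 points above t theory. Fidelity is also a ratio over a limited set of components, so it is discrete, and neither model represents that. Only the 97.5% at exactly 80% is free of the SD, and it needs normality.

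A third reply is that a mean and range is an acceptable descriptive summary for about 20 participants. It is, but the protocol promised a 95% CI and the SAP gives no reason for dropping it.

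**Conclusion.** The concern holds and is minor. The protocol's rule is backwards as written: at a true mean of exactly 80% it declares use above 80% in 97.5% of trials instead of 2.5% (t theory). How often it would mislead below 80% depends on the unknown SD. Near 10 points it does little harm when use is clearly poor (0.6% to 2% at a true mean of 70%). At 20 points or more it misleads often (39% to 73% at the same mean).

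Harm arises only if a report applies the rule. Under the SAP alone no wrong conclusion follows; the loss is a mean reported without a measure of precision. Fidelity is a one-arm process measure, so nothing here touches the primary outcome, the randomized comparisons or the sample size.

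**What to change.** Add one line to the SAP: the decision rule in protocol Hypothesis 1 is withdrawn and fidelity is descriptive. In section 2.3.4, report the mean proportion with its 95% CI as well as the range, with no success threshold. SAP section 2.2.2 gives a study end date of 5/24/21, before the SAP was written, so label this a correction made after study end and say whether fidelity data had been seen.

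The cost is two or three sentences and no new data. No power is lost, because no test remains. The t interval is approximate for a bounded measure: in the beta simulation at a true mean of 80% it covered 92.6% to 94.5% (n = 22) and 92.1% to 94.4% (n = 18), which should be noted.

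Only if the sponsor keeps Hypothesis 1 as a test should the rule be changed to require the lower 95% limit to exceed 80%. That makes the claim much harder to support:
- At n = 22 the observed mean must exceed about 84.4%, 88.9% or 93.3% for SD 10, 20 or 30 (85.0%, 89.9% or 94.9% at n = 18).
- At a true mean of 85% the chance of support is 61%, 20% or 11% at n = 22 (52%, 17% or 10% at n = 18).
- At a true mean of 90% it is 99% or 61% at n = 22 (98% or 52% at n = 18) for SD 10 or 20.
- The error rate at a true mean of 80% is 3.9% to 7.2% in the beta simulation, against a nominal 2.5%.
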